Informed consent will be obtained from all subjects participating in this study. Ethical approval was approved by the University Health Network (UHN) Research Ethics Board(Approval Number: 18-6163). The approval form is included in the supplementary files of this submission. This study is registered under the National Institutes of Health ClinicalTrials.gov.

Consent for publication:

Not applicable.

Availability of data and material:

The datasets used and/or analyzed during the study will be available from the corresponding author upon reasonable request.

Trial Status:

Protocol version and date: Version 2, May 1,2019

Recruitment: Starting June 2019- November 2019

The Delsys Trigno EMG machine has been ordered. The pharmacy has approved the intended capsaicin formula that will be used in the experiment. Participants will be recruited from June 2019- November 2019

Competing interests:

The authors declare that they have no competing interests.

Funding:

This study is being conducted with no external funding and was instead funded from the Toronto Rehabilitation Institute.

Authours' Contribution:

All authors (VE, KM, DK) contributed to the study design; drafted, reviewed and finalized the study protocol; critically revised the manuscript and approved the final manuscript.

References

1. Srbely JZ. New trends in the treatment and management of myofascial pain syndrome. *Curr Pain Headache Rep* 2010;14(5):346-52.

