Methods: The study conforms to the Consolidated Standards of Reporting Trials recommendations. Ethical approval will be sought from the University Health Network (UHN) Research Ethics Board. This proposed study is a single centered, factorial, randomized placebo-controlled trial with two independent variables, depth of capsaicin application and dose of capsaicin, for a total of four treatment arms and two control treatment groups.

Discussion: This will be the first study that assesses the B-mode ultrasound image texture of induced sensitized muscles, and will provide more evidence on muscle motor unit activity and regional changes of central sensitization. Findings from this study may support one of few hypotheses proposed delineating the involvement of central sensitization in the development of trigger points.

Trial Registration: Name: National Institutes of Health ClinicalTrials.gov.
Identifier: NCT03944889
Date of Registration: May 07 2019
URL: <https://clinicaltrials.gov/ct2/show/NCT03944889>

Keywords: myofascial pain syndrome; ultrasound; image texture; electromyography; central sensitization; trigger points

List of Abbreviations:

US: Ultrasound

EMG: Electromyography

MPS: Myofascial pain syndrome

MTrP: Myofascial trigger points

SEA: Spontaneous endplate activity

Background

Myofascial pain syndrome (MPS) is a prevalent chronic pain disorder primarily characterized by myofascial trigger points (MTrP). MTrP are stiff taut bands of muscle distinguished by hypersensitivity on palpation and local twitch responses on snapping palpation.[1] A current clinical challenge in chronic pain care, applicable to myofascial pain, is early detection and effective treatment targeting the underlying pathophysiology.

There is limited knowledge on the pathophysiology and mechanisms underlying MTrP and its development. Ultrasound studies have been able to characterize trigger points[32,45,46], however there are some contradictory findings on whether these areas are hyperechoic or hypoechoic[45,46]. More recently, texture feature analysis have been shown to differentiate between healthy and MPS as well as active and latent trigger points[32]. Trigger points are typically located within the region of the muscle belly, where there is a high distribution of motor endplates.[2,3] Seventy-one percent of acupoint locations in the body, which are regions associated with motor points, motor endplates, or major motor nerve pathways overlap with common MTrP.[4]

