Investigations assessing neuronal responsivity to noxious stimuli have demonstrated increased sensitization at the region of primary nociception and the development of a secondary nociceptive field.[13-15] This has been confirmed using EMG and quantitative sensory testing methods to assess the activity of sensory nociceptive, mechanoheat, and chemoreceptive nerve

fibers following the injection or application of capsaicin.[13-15]. Many other factors are likely involved in the chronic pain patient including disordered ascending and descending signals within the central nervous system, termed nociceptive pain by the IASP.[18,19,49] Dideriksen et al.[16] and Falla et al.[17] demonstrated that motor unit potentials reduce in amplitude following the injection of nociceptive hypertonic saline into the upper trapezius muscle. This is in line with the EMG characteristics of MTrPs cited earlier.[7,8] However, other studies, such as the study directed by Birch et al. (2000), present contradictory results, indicating that no significant differences in motor unit discharge rates were found. Studies assessing the EMG activity of trigger points failed to locate the aberrant activity that characterizes MTrP using surface EMG but were able to demonstrate the presence of SEA, intermittent spikes in active MTrP, as well as activity associated with local twitch responses using intramuscular EMG recordings due to the method's specificity.[5]

In regards to MTrP structure, Shankhar et al. (2012) was able to identify taut bands of MTrPs using 3D and 2D ultrasound[47]. They discovered that the muscle fascicles surrounding the taut band presented a different appearance than the adjacent healthy muscles. The study identified MTrPs as hyperechoic regions, as in another study confirmed by Lewis et al.(1999)[46]. In contrast to these studies, Sikdar et al. (2008) noted that MTrPs appear as hypoechoic elliptical regions within the ultrasound image[48]. Although there is some evidence on the changing structure of myofascial trigger points, to the best of our knowledge, there has been no evidence of how central sensitization affects muscle structure through image analysis. There is a need for a study that measures specific B-mode ultrasound textural changes within sensitized areas, as well as motor unit activity responses in the muscle following sensitization.

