The purpose of this study is to determine whether sensitizing healthy muscle using capsaicin, a chilli pepper extract, induces a regional change in ultrasound texture features of the targeted muscle, or of the muscles in that are in close proximity. This regional change will be accompanied by electromyography (EMG) recordings to confirm the presence of abnormality. Central sensitization will be induced using topical capsaicin and injectable capsaicin at three different concentrations. This is an exploratory trial that aims to provide preliminary evidence on whether central sensitization is a direct cause of taut band and MTrP development.

Our specific research questions are followings:

- a. Does sensitization cause a significant regional change in the texture features of the targeted muscle or surrounding muscles? Our hypothesis is that there will be a structural change within the sensitized or adjacent muscles.
- b. Does capsaicin induced sensitization elicit a change in motor unit action potential(MUAP) amplitude by approximately 20 to 25% within the region of experimentally induced central sensitization or in the region of texture feature changes? Our hypothesis for this portion of the study is that sensitization modifies the anterior horn cell activity which will be measured by the amplitude of the potentials and the change in texture features.
- c. Does capsaicin induced sensitization elicit continuous electrical activity as observed in MTrPs? This tests the hypothesis that sensitization creates the presence of continuous low amplitude action potentials.
- d. Does capsaicin induced sensitization influence the rate of recruitment of motor units in the muscle within the region induced? Does this occur within the regions identified by the

changes in texture features? The recruitment of motor units is normally expected to follow the Henneman size principle.[20-23] Our hypothesis for this portion of the study is that sensitization will cause an aberration in recruitment. If this is demonstrated, then there is modification of the normal processing at both dorsal and ventral horns of the spinal cord.

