The Sonosite Ultrasound machine located at the Toronto Rehabilitation Institute clinic will be used. The ultrasound probe will be placed onto the trapezius before and after the sensitization is induced and an ultrasonic image will be captured. Texture feature analysis will be performed using MATLAB and the Signal Processing Toolbox. Analyses will include first order parameters such as mean and standard deviation of the pixel level values, as well as second order parameters, which provide details on the spatial distribution of pixel values. These include co-occurrence and run-length matrices, local binary pattern and blob analysis[Quant text ref].

Measurement of motor unit activity using EMG

The Delsys Trigno surface EMG system will be used in this experiment. The system offers the benefit of having a 4-pin mini-grid that can extract individual motor unit data, without causing participants discomfort. The analysis will also be complemented by the use of intramuscular EMG, since it offers high location specificity when measuring EMG activity, while only a local region is analyzed. The intramuscular EMG data will be analyzed by a Cadwell Sierra Wave device.

The anatomical location for electrode placement, along the C7-acromion line, will be identified for each participant. Baseline EMG measurements, as well as the ultrasonic images will be taken from the upper trapezius muscle to obtain the baseline motor unit recruitment curve. The trapezius muscle was chosen for study since it is a common site for MTrPs, given the high load cervical muscles carry as well as the general increase sedentariness that perpetuates poor posture and cervical muscle strain, leading to trigger point presentation. Furthermore, the

trapezius muscle has been used frequently in previously published work, which analyze motor unit parameters, power spectrum and amplitude measurements.[31,32,33]

sEMG Analysis

After the identification for electrode placement and the captured baseline ultrasonic images, the area will be cleaned with alcohol and water. The Delsys Galelio sensor will be placed directly on the identified area. The EMG sensor (bandwidth of 20-450Hz) consists of 4 metal contacts for detecting the signal at the skin surface. Both the right and left sides of the trapezius will be measured.

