The Delsys Trigno system, which includes sensors, the Trigno base station, and the EMGworks software will be used to decompose the acquired EMG signals into individual motor units. The following parameters will be analyzed: the firing times and frequency of individual motor units, motor unit action potential amplitude and shapes[36-38], the root mean square value (RMS) of each channel and of the entire signal[16], the coefficient of variation for force steadiness[39], and the centroid of the EMG signal in the cranial-caudal and the medial-lateral directions[16]. This will be repeated for each contraction.

Intramuscular EMG analysis

A 27g monopolar electromyography needle will be placed into the midbelly of the upper fibers of the trapezius muscle using ultrasound guidance. The intramuscular EMG signals will be measured using Cadwell Sierra Wave. Since this system does not offer motor unit decomposition, we will use the intramuscular EMG analysis to provide us with more details of the gross EMG measurements such as the overall RMS value, the coefficient of variation for force steadiness, and the centroid measurements.

Determination of Central Sensitization:

Before measuring outcomes, approximately 20 minutes after capsaicin application we will analyze the area of secondary hyperalgesia for each study subject, then determine whether central sensitization has in fact been induced. The presence of central sensitization is confirmed by expansion of the receptive field and area of secondary hyperalgesia beyond the 25 cm² initial application area. If it has, the study participant will undergo the rest of the experimental methodology. If it has not, the capsaicin will be applied once more and the region of secondary hyperalgesia will be remeasured in 20 minutes later. The above described process for confirming the presence of central sensitization will take place again. If the study participant has not had sensitization at this stage they will be withdrawn from the study.

Primary Outcomes

The primary outcome measures:

1. Textural regional changes
2. Recruitment and Amplitude regional changes

These will be recorded for each arm of the study, please see figure 1.

Secondary outcomes:

1. A record of adverse events

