texture features will be computed in MATLAB and principal component analysis will be computed to reduce the variables. A repeated measures MANOVA will be applied for each intervention group. To test the change in EMG within and between groups a repeated measurement ANOVA will be applied considering each intervention group as a factor. The dependent variable would be considered as pain intensity, duration, and area of pain in separate analysis. Data distributions would be first checked with the Shapiro-Wilk to conform the normal distribution of the data. Additionally, we will test for the homogeneity of variance using Mauchly's test as well as correcting the degrees of freedom if necessary [40]. If the assumption of normality not met, for all skewed data an appropriate transformation will be used. We will construct univariate and multivariable linear regression models of differences in EMG amplitude (differences between after and before) as a function of intervention groups when adjusted for important covariates. Due to small sample size in each group, there is not possible to adjust for several covariates. Therefore, in a univariate model we will find the most important ones. For initial selection of relevant variables, all variables with a p-value ≤ 0.2 in the univariate analysis will be selected and retained in the multivariable analysis.

All Statistical analyses will be conducted with SAS for Windows (version 9.3; SAS Institute, Inc, Cary, NC). Using a two-sided test a P-value ≤ 0.05 will be considered as statistically significant.

Discussion

This will be the first study that assesses the effect of capsaicin induced central sensitization on ultrasound texture features and muscle motor unit activity. Findings from this

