fiber' presentation and metabolic changes such as ischemia, hypoxia, and insufficient ATP.[7,41] This may result in disturbed calcium homeostasis and the development of the muscle contracture known as the trigger point. Low threshold motor unit activity was demonstrated in a number of articles assessing the effect of continued muscle contraction and psychologically demanding tasks—muscle overexertion and persistent psychological stress are theorized triggers for chronic pain and trigger point development.[43,44] The sustained contracture in the muscle maintains the hypoxic and acidic environment, leading to peripheral and central sensitization of neurons in the associated spinal segment.[7] This suggests an endogenous and exogenous cause for the trigger points. Under the premise of the Cinderella hypothesis, it would be expected to observe sustained low threshold motor unit activity with central sensitization.

The neurogenic hypothesis is distinct from the integrated and Cinderella hypotheses as it posits trigger point development is a result of endogenous central sensitization.[1] Central sensitization would result from persistent nociceptive input from other peripheral mechanic or systemic pathologies leading to neurogenic inflammation, such as trauma or endocrine disease. Subsequently, inflammatory and algogenic substances would be released from peripheral nociceptors onto tissue and sensitizing the region. Sensitization of motor and sensory neurons innervating somatic muscle may lead to the phenomenon of trigger points. Ultimately, the neurogenic hypothesis stipulates the trigger point is a secondary outcome central sensitization, which is the primary pathology. Textural changes throughout the induced muscle, as well as the regional muscles would support this hypothesis. Continuous low threshold motor unit activity would also be an anticipated observation as neurons will be increasingly sensitized. It would also be expected to observe increased low threshold motor unit activity in remote muscles that present

with signs of central sensitization, e.g. hyperalgesia, however this is outside the scope of this article.

Limitations and Conclusions

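### The planned texture test can show that texture changed but not in which direction, yet the Discussion would count undirected texture changes as support for the trigger-point hypothesis

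*Combined protocol and SAP*

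**What the plan says.** All references are to the combined protocol and SAP.

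- **Aim (Background).** The trial "aims to provide preliminary evidence on whether central sensitization is a direct cause of taut band and MTrP development". The narrower purpose stated just before this is to find out whether capsaicin sensitization produces a regional change in texture features.
- **Hypothesis (Background, research question a).** "Our hypothesis is that there will be a structural change within the sensitized or adjacent muscles". No feature or direction is named.
- **Outcome (Primary Outcomes).** The first primary outcome is "Textural regional changes", with nothing further.
- **Measurement (Ultrasound analysis).** The features include "first order parameters such as mean and standard deviation of the pixel level values", plus co-occurrence, run-length, local binary pattern and blob measures.
- **Analysis (4. Statistical analysis plan).** "principal component analysis will be computed to reduce the variables", followed by a repeated measures MANOVA for each intervention group, two-sided at 0.05. The number of components and the rule for retaining them are not given.
- **Reading of the result (Discussion, on the neurogenic hypothesis).** "Textural changes throughout the induced muscle, as well as the regional muscles would support this hypothesis". The same paragraph also expects continuous low-threshold motor unit activity.
- **What is known about appearance (Background).** Two cited studies describe trigger points as hyperechoic. Another reports that "MTrPs appear as hypoechoic elliptical regions within the ultrasound image". The Background also says that texture features can tell healthy from myofascial-pain muscle, but names no feature and no sign.

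**The concern.** The trial's wider aim concerns trigger points, but the texture question, outcome and test concern change of any kind. The step from one to the other is made only in the Discussion, which says where the change should occur and not which way it should go.

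Nothing else in the plan supplies a direction. People with palpable trigger points are excluded, so there is no internal reference group. Question c compares with trigger points, but for EMG only. Principal components follow the directions of greatest variance in the volunteers' images, which need not be the direction that separates healthy from myofascial-pain muscle. A component's sign is also arbitrary, so an unplanned reading of component means afterwards could be made to fit either account.

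At stake is the interpretation of a primary outcome. A significant result could be cited in favour of the trigger-point hypothesis even if the muscle had moved away from trigger-point texture, or along an unrelated axis.

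**Working it through.** The plan gives no figure for the texture analysis. Its sample size of 70 is for a repeated measures ANOVA and is not affected by this point.

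**1. Is the test blind to direction?**

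With two time points in one group, the MANOVA is a paired Hotelling test on the component change scores. With n participants, p components, mean change vector m and covariance matrix S:

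T² = n · m′S⁻¹m, and F = [(n − p) / (p(n − 1))] · T² on p and n − p degrees of freedom.

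Replacing every change by its negative turns m into −m and leaves S as it is, so T² is unchanged. In a test sample of 12 with 3 components, p = 0.2092 for the changes and 0.2092 for their mirror image. This property needs no assumption about group size, number of components or effect.

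**2. What does that mean for rejection rates?**

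Assumed, not in the documents: 12 per group (84 / 7; the arm count is stated inconsistently), 3 retained components, and a true shift of 0.8 SD of the change score.

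- Noncentrality: 12 × 0.8² = 7.68, on 3 and 9 degrees of freedom.
- Power from the noncentral F: 0.444.
- Simulation, 5,000 runs each: 0.445 for a shift toward a reference direction, 0.445 away from it, 0.443 along an unrelated axis.
- Range over n = 10 to 14 and 2 to 4 components: 0.26 to 0.65, and in each case the same for every direction.

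**3. Would a single directional index do better?**

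Assumed: a shift of 0.5 SD and 12 participants, so noncentrality is 12 × 0.25 = 3.0 if the whole shift lies on the index. If the index is at angle θ to the true shift, it sees only 0.5 · cos θ, and noncentrality is 3.0 · cos²θ. All tests are two-sided at 0.05.

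| Test | Noncentrality | Power |
|---|---|---|
| MANOVA, 3 components | 3.0 | 0.19 |
| Index, fully aligned | 3.0 | 0.35 |
| Index, 45° off | 3.0 × 0.5 = 1.5 | 0.20 |
| Index, 60° off | 3.0 × 0.25 = 0.75 | 0.12 |

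A pooled comparison of 56 capsaicin with 28 control participants shows the same pattern. It assumes six groups of 14 (84 / 6), four of them active, and is not the planned test. Power is 0.40 for 3 components, against 0.57 for an aligned index, 0.33 at 45° and 0.19 at 60°.

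The index is therefore better only if it lies close to the true change. The documents do not say how an acute capsaicin effect relates to myofascial-pain texture.

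**The case against.** The strongest reply is that a non-directional question is the right one here. The trial calls itself exploratory, reports of echogenicity conflict, and the Background says image analysis has not yet shown how sensitization affects muscle structure. The stated purpose is to detect a regional change, and the MANOVA answers that. A null result would be informative too. All of this stands.

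Three further replies also stand in part.

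- The Discussion does not accept just any texture change. It asks for change throughout the induced and regional muscles and expects an accompanying EMG pattern. Neither gives the texture change a direction.
- Equal rejection rates either way are a feature of every two-sided test, and direction normally comes from the estimate. That is so, but here no signed estimate or rule for reading one is prespecified.
- Limitations and Conclusions says that the results do not generalize directly to people with myofascial pain. That limits the population and leaves the Discussion's reading of texture change as it is.

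A reader might infer that the texture outcome has no bearing on the aim, or that the MANOVA should give way to one directional index. The documents support neither. An undirected change is weak evidence rather than none. The features and signs needed for an index are not in the documents, and its gain in power depends on an alignment that nobody can confirm in advance.

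**Conclusion.** The point holds as one of interpretation. The texture analysis is a valid test of whether texture changed. It cannot separate a change toward trigger-point appearance from one away from it, and the plan fixes no reference that would allow this. The Discussion's statement of support therefore goes further than the planned analysis can.

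The sign-blindness is exact and rests on no assumption. The rejection rates (0.44 in every direction, range 0.26 to 0.65) illustrate it under assumed group sizes, component counts and a 0.8 SD shift. They are not estimates of this trial's power.

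The plan does not say that a significant MANOVA alone will be reported as trigger-point-like structure, so that outcome is a risk and not a stated intention. Nor should an advantage in power be claimed for a directional index.

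**What to change.** 1. **4. Statistical analysis plan.** Keep the principal component analysis and MANOVA. Add that a significant result will be reported as evidence that texture changed, and no more.
2. **Same section.** Prespecify, for each imaged muscle, the signed pre-to-post change, capsaicin minus control, with a 95% CI. Do this for mean pixel level and for the other features named under Ultrasound analysis. Mean pixel level then shows whether muscle became brighter or darker. The planned MANOVA is run group by group, so the contrast with control has to be written in explicitly.
3. **Discussion.** Amend the sentence on the neurogenic hypothesis so that a texture change counts as support only if its direction matches a trigger-point pattern fixed before the images are analysed. The cited healthy-versus-myofascial-pain texture work is the natural source ("texture feature analysis have been shown to differentiate between healthy and MPS as well as active and latent trigger points[32"). If no pattern can be fixed from it, or the reports conflict as they do for echogenicity, describe the texture result without trigger-point inference.
4. **Optional.** A single directional index may be added as a supportive analysis, with no claim of greater power.

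The cost is wording, a few more reported estimates from features already computed, and a narrower conclusion from a significant MANOVA. No new images are needed.

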This experimental protocol will be carried out at the [name] Lab, Toronto Rehabilitation Institute to ensure any medical emergencies can be promptly cared for. Following the completion of the preliminary intake forms and participant debriefing, informed consent will be obtained. Each participant will be seated upright with their hands comfortably on their lap in a chair that has a high supportive back. They will be asked to relax their neck and shoulder muscles. A member of the research team will then apply the inclusion and exclusion criteria. The presence of a MTrP will be assessed by palpation of the upper trapezius muscle since this is the current method utilized in clinical practice. If there is a MTrP, then they will be asked to withdraw from the study since they do not satisfy the inclusion and exclusion criteria.

Participants will sit on a chair with one arm extended downward, and with the other arm on an armrest of the chair. The extended arm will be fixed by a wristcuff and a chain down to the floor, with a loadcell between the floor and the end of chain. The loadcell will measure the exerted force. The anatomical location for ultrasound probe and electrode placement will be identified for each participant. The ultrasound probe will be placed on 3 muscles: the trapezius, the supraspinatus, and the infraspinatus. Two ultrasonic pictures will be taken of each. Care will be taken to image the region of the muscle that was not mechanically impacted by the insertion of the needle or injection of the substance. The area will then be cleaned with alcohol and water. The Delsys Galelio surface sensor, and the intramuscular needle electrode will be placed directly on the trapezius' identified area. Participants will be asked to gently contract their trapezius muscle. They will be instructed to perform a gradually increasing contraction in isometric condition, in a controlled manner with a monitor showing the exerted force as well as the target force. They will hold this contraction at 30% of their maximal voluntary contraction, and then

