perform a gradually decreasing contraction to rest. This will be performed four times for each type of study intervention and before as well as after each intervention, namely topical control cream, topical capsaicin at 50ug and 100 ug, injection of the superior aspect of the superior fascia followed by intramuscular injection with these two concentrations of capsaicin. The placement of these latter will be verified by ultrasound guidance. The intramuscular needle will then be removed and participants will be bandaged and cared for appropriately by the expert physician performing the experiment. Following this, ultrasound pictures will be taken again from the same muscles mentioned previously. Participants will be re-examined to determine if there were any adverse effects from the experimental procedures. If any occurred, then these will be carefully managed by the medical members of the research team and recorded. Participants will be asked to remain at the lab for an additional 30 minutes to ensure they are well prior to leaving (Figure 2).

Central sensitization and measurement techniques

Inducing central sensitization

Central sensitization will be induced using capsaicin according to the established technique.[13,24,25] It induces increased pain severity at high doses relative to heat and elicits a dose dependent pain responses, allowing for more easily quantifiable measurements.[26] Capsaicin delivery induces both primary and secondary nociception suggesting that central mechanisms are involved in the nociceptive response, also termed as central sensitization.[13,14] Previous evidence has confirmed that capsaicin can sensitize nociceptive and mechanoheat receptors outside of the region of primary hyperalgesia, with speculation that it can also sensitize chemonociceptive receptors.[13] Therefore, capsaicin can effectively be used to induce central sensitization.

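### Questions b and d place EMG change in the region of texture change, but no planned analysis or matching rule links the two measurements

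*Combined protocol and SAP*

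**What the plan says.** **Questions.** The purpose statement at the end of the Background concerns a regional texture change in the targeted muscle or its neighbours, and adds: "This regional change will be accompanied by electromyography (EMG) recordings to confirm the presence of abnormality". Question b asks whether MUAP amplitude changes by about 20 to 25% "within the region of experimentally induced central sensitization or in the region of texture feature changes". Question d asks about recruitment in the sensitised region, then adds a second question beginning "Does this occur within the regions identified by the", which refers to the texture changes.

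**Measurement.** Experimental Protocol: "The ultrasound probe will be placed on 3 muscles: the trapezius, the supraspinatus, and the infraspinatus". For EMG, the "surface sensor, and the intramuscular needle electrode will be placed directly on the trapezius' identified area". The section on measuring motor unit activity gives the landmark: "The anatomical location for electrode placement, along the C7-acromion line, will be identified for each participant". After the contractions, the needle is removed and then: "Following this, ultrasound pictures will be taken again from the same muscles mentioned previously". There is also an imaging precaution: "Care will be taken to image the region of the muscle that was not mechanically impacted by the insertion of the needle".

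**Analysis.** The Statistical analysis plan sends texture features to principal component analysis and a repeated measures MANOVA, and EMG to a repeated measures ANOVA. EMG amplitude change is also regressed on intervention group and unnamed covariates.

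**The concern.** The texture-region parts of b and d are questions about co-occurrence: does the motor unit change appear where the texture change appears? Two analyses that never meet cannot answer that. Texture might change in some participants and EMG in others. Both tests could still reach P ≤ 0.05, and the report could then present EMG as bearing out the structural change.

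Two measurement gaps add to this. Nothing records how the imaged region relates to the tissue under the sensor. A texture change in the supraspinatus or infraspinatus, which the purpose statement and question a allow for, would have no EMG to set beside it.

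**Working it through.** **1. Questions set against what is measured and analysed.**

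| Part of the question | Data described | Planned analysis |
|---|---|---|
| b and d, sensitised region | Trapezius EMG before and after | EMG ANOVA; regression for amplitude |
| b and d, texture region, trapezius | Texture and EMG, both before and after | Each separately; none joint |
| b and d, texture region, supraspinatus or infraspinatus | Texture only | None possible for EMG |

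The regression does not fill the gap in the second row, because texture is not named as a predictor. Nor does the sentence on dependent variables after the EMG ANOVA, which lists pain intensity, duration and area.

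**2. What a participant-level association could detect.** The plan gives no figure for this. Its 70 participants (84 recruited) were derived for a repeated measures ANOVA, and I take those numbers as given. Inputs are 80% power and two-sided alpha 0.05 (Sample size calculation; Statistical analysis plan), so the z values sum to 1.9600 + 0.8416 = 2.8016. With N participants and k arms adjusted for, the detectable partial correlation is

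r = tanh(2.8016 / √(N − 3 − (k − 1))).

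- N = 70, k = 6: tanh(2.8016/√62) = 0.34
- N = 84, k = 6: tanh(2.8016/√76) = 0.31, which assumes no attrition
- N = 70, k = 7: tanh(2.8016/√61) = 0.34
- N = 70, k = 9: tanh(2.8016/√59) = 0.35
- N = 70, no arm adjustment: tanh(2.8016/√67) = 0.33

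The document gives six, seven and nine groups in different places; the result hardly depends on which is used.

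The section Determination of Central Sensitization withdraws participants who are not sensitised. Read literally, this could remove the controls. On that assumption four of six arms remain, 70 × 4/6 ≈ 46 participants:

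- N = 46, k = 4: tanh(2.8016/√40) = 0.42

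For an exploratory estimate the interval matters more than power. Around r = 0, the 95% CI half-width is tanh(1.96/√62) = 0.24 with 70 in six arms, and tanh(1.96/√40) = 0.30 with 46 in four.

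**3. Why the association cannot stand in for a test of effect.** Suppose, as an illustration, that capsaicin shifts both outcomes by the plan's 0.5 SD in four of six equal arms, and that within arms the two changes are unrelated. (With the plan's correlation of 0.5, the SD of a change is √(2 × (1 − 0.5)) = 1 times the SD of the measure.) The arm-adjusted correlation is 0. The unadjusted one is (2/3)(1/3)(0.25) / (1 + (2/3)(1/3)(0.25)) = 0.0556/1.0556 = 0.05. A true effect on both outcomes can leave the association close to zero.

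**The case against.** A reader might infer that EMG cannot be co-located with a texture change at all, because electrodes are sited before any change is imaged and the images avoid needled tissue. The documents do not support that.

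- Experimental Protocol identifies the location for the probe and for the electrodes together, then cleans that area and places the sensor there. Some overlap may well be intended.
- MUAP amplitude and firing come from decomposing the surface signal. The needle system offers no decomposition. The imaging precaution reads as a guard against artefact and does not bar imaging of muscle under the surface sensor.
- Any before-after EMG comparison needs its site fixed at baseline, so siting the electrodes first is not a fault.
- The purpose statement and question a use region partly at the level of whole muscles. On that reading, trapezius texture and trapezius EMG are both available.

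It can also be said that the trial is exploratory, that texture and EMG are listed as separate primary outcomes, and that the purpose statement speaks of confirming abnormality, not of confirming the texture change itself. Question b is an either-or, so its sensitised-region half stands. Texture could be among the unnamed covariates.

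All of this narrows the point without removing it. Even with the trapezius as the region, no planned analysis relates the two changes. No rule ties image to sensor, and the other two muscles have no described EMG. Nothing says that texture is a covariate.

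**Conclusion.** The point holds as a gap in analysis and specification. The texture-region part of question b and the second question in d are not answered by the plan as written. For the trapezius the data would exist and only the linking analysis is missing; for the other two muscles the EMG is not described either. The stronger conclusion, that the design rules out any answer, goes further than the documents do.

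An association on the planned data would have modest precision: detectable partial r about 0.34 with 70 analysed in six arms, and about 0.42 under the assumption that only about 46 in four active arms remain. The order of procedures is taken from the text, because the timeline figure is not shown.

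**What to change.** 1. Reword the texture-region parts of b and d: in the trapezius, is a participant's before-after change in texture associated with the change in MUAP amplitude, and with the change in recruitment?
2. Name one trapezius texture score in advance, for example the first principal component. State how the two pictures and four contractions become one value per time point, and which side is paired, since surface EMG is taken on both sides.
3. Pre-specify one exploratory analysis per EMG outcome (MUAP amplitude, recruitment) relating its change to the change in the texture score. Report estimates with 95% CIs both with and without adjustment for randomised arm: the adjusted one shows only within-arm association, while the unadjusted one also carries any shift between arms.
4. Do not make the arm-adjusted association a condition for claiming an effect on either outcome. Equally, do not describe EMG as confirming texture change in the same region on the strength of separate tests alone.

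The cost is protocol and SAP wording and one short analysis per EMG outcome, with no new data. The downsides are that the spatial wording is given up (a participant-level association does not show that the changes share a location), that the result is exploratory, and that the intervals will be wide.
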